7.10 TOXICITY ASSESSMENT

Any subject who receives at least one dose of study therapy will be evaluable for toxicity endpoints. Each subject will be assessed for the development of toxicity according to the timeframe referenced in the Schedule of Events table. Toxicity will be assessed according to CTCAE v 5.0 criteria. Also refer to [Table 6-2](#) for the dose modification and management of leronlimab (PRO 140) for any toxicity.

All subjects will be followed for adverse events for 30 days after last dose of leronlimab (PRO 140), or until the subject starts a new treatment, whichever occurs first.

Subjects who discontinue treatment for unacceptable adverse event(s) will be followed until resolution or stabilization of the adverse event (i.e. the grade is not changing). If a subject stops treatment due to unacceptable adverse event(s) but has not demonstrated disease progression, then the subject will be followed with imaging studies every 9 weeks until the time of progression radiographically according to RECIST v1.1 criteria.

7.11 CLINICAL LABORATORY ASSESSMENTS

Blood samples will be collected for analysis of the following parameters:

- Biochemistry and Complete Blood Count (CBC) Parameters: At Screening, T1 and every 3 weeks thereafter, and at the end of treatment (EOT).
- Serum pregnancy test (for female subjects of childbearing potential): At Screening
- Urine pregnancy test (for female subjects of childbearing potential): T1 and every 3 weeks thereafter
- CTC and CAML Analysis: T1 and every 3 weeks thereafter and at the end of treatment (EOT).

Note: CBC, biochemistry, and urinalysis testing schedule (i.e., every 21 days) is allowed to be modified by the treating oncologist (or Investigator) based on standard of care chemotherapy regimen. Must be performed at least once every 28 days (4 weeks).

All laboratory reports will be reviewed by the Investigator. Abnormal results that are considered by the Investigator to be clinically significant, will be recorded as adverse events. If in the Investigator's judgment, in order to make the determination of clinical significance the testing may be needed to be repeated. Validated, quality-controlled laboratory data will be transferred to the main database for analyses.

Table 7-2: Central Lab Parameters

CBC Parameters	Biochemistry Parameters	Urinalysis
Hemoglobin	Liver Function Tests	pH
Hematocrit	Total Bilirubin	Appearance
RBC count	Direct Bilirubin	Color
WBC count	Alkaline Phosphatase (ALP)	Specific gravity
WBC Differential	Alanine Aminotransferase (ALT) (or SGPT)	Turbidity
Absolute lymphocyte count	Aspartate Aminotransferase (AST) (or SGOT)	Ketones
Absolute neutrophil count	Albumin	Bilirubin
Platelet count	Total Protein	Blood
Miscellaneous		Glucose
Renal Function Tests		

Serum pregnancy test	Blood Urea Nitrogen (BUN)	Protein
Urine pregnancy test	Creatinine	Nitrites
(for female subjects of childbearing potential)	Electrolytes	Urobilinogen
Tissue for CCR5 expression (archival or fresh biopsy)	Sodium	Leukocyte esterases
CTC and CAML- Creatv Microtech	Potassium	Microscopic exam includes bacteria, cast, crystals, epithelial cells, RBC and WBC.
	Chloride	
	Calcium	
	Bicarbonate	
	Other:	
	Glucose, Random, Serum	

7.11.1. Correlatives/Special Studies

Correlative Samples - Details for Lab Manual		
Correlative study (sample type)	Tissue CCR5 Staining*	CTC and CAML
Mandatory or Optional	Mandatory	Mandatory
Timing (+/- windows)	Archival or fresh	1-3 days
Volume Needed (blood only)	N/A	20 cc whole blood for CTC and CAML
Tube type needed (blood only)	N/A	CellSave tube to be filled up completely
Tissue thickness and/or # slides (tissue only)	5 μ (No. of slides- TBD)	N/A
Processing center (e.g. PCF- CTU)	PCF	Creatv MicroTech, Inc
Sampling/ processing instructions	See lab manual	See lab manual
Shipping/delivery info	Medical College of Wisconsin (see below)	Creatv MicroTech, Inc
Storage needs	Paraffin slides	See lab manual
Analysis center	See lab manual	See lab manual
Assay methodology	IHC	See below

* Archival breast tissue (primary or metastatic site) will be collected from all patients at the pre-screening period and analyzed for presence of CCR5. Note: If no archival tissue is available, fresh core or excisional biopsy to be done of the primary or metastatic site.

7.11.1.1 Sample Collection Guidelines

Please refer to laboratory manual for more details

7.11.1.3 Assay Methodology

CTCs and CAML using CellSieve™

The CellSieve™ microfiltration assay isolates circulating tumor cells (CTCs) and circulating cancer-associated macrophage-like cells (CAMLs) by size exclusion, identifying CTCs and CAMLs by their morphological features and the phenotypic expression of CCR5, cytokeratins 8, 18, and 19, CD45 and DAPI. Peripheral blood (7.5 mL) collected in CellSave preservative tubes is prefixed for 15 min, placed into the 30-mL syringe, and drawn through the filter in ~3 min. The filtration instrument utilizes negative pressure to draw the sample through the filters at a gentle continuous rate. The filter is then washed, postfixed, and permeabilized for 15 min. The filter and cells are stained with an antibody mixture and blocking buffer of FITC-conjugated anti-cytokeratin 8, 18, 19, phycoerythrin (PE)-conjugated CCR5, and Cyanine5-conjugated CD45 (Creatv MicroTech, Inc.).

CTCs are CD45 negative cells with a pleomorphic nucleus and a filamentous cytokeratin positive phenotype. CAMLs are large (21–300 µm in length) and morphologically distinct from CTCs. CAMLs are identified as single cells with an enlarged nuclear profile (14–64 µm in diameter) or separated polymorphic nuclei contained within the cell. In addition, the nuclei are surrounded by a larger CD45 signal. CAMLs can be identified further by vacuoles containing DAPI+ and/or cytokeratin.

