3.2 STUDY POPULATION

The target population for this study is subjects with histologically or cytologically confirmed diagnosis of CCR5+ locally advanced or metastatic solid tumors.

This will be a multicenter trial. A total of 30 subjects will be needed for this trial.

Eligibility will be evaluated by the study team according to the following criteria. Eligibility waivers are not permitted. Subjects must meet all of the inclusion and none of the exclusion criteria to be registered to the study.

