3.3 ELIGIBILITY CRITERIA

3.3.1. Inclusion Criteria

Subjects are required to meet all of the following criteria for enrollment into the study:

1. Must have a histologically or cytologically confirmed diagnosis of locally advanced or metastatic solid tumors:
 - a. who have disease progression on standard therapy,
 - b. who are receiving a standard anticancer treatment but no subsequent approved treatment would be available upon progression,
 - c. who are unable to receive standard therapy, or
 - d. for whom standard therapy does not exist.
2. Demonstrate CCR5 + by IHC (>10% of primary or metastatic tumor cells shows membranous staining and/or high predominance of CCR5+ tumor-infiltrating leukocytes completed at the reference laboratory of [name] at Medical College of Wisconsin).

Note: This test will be done as part of the pre-screening period. It will be performed in archival metastatic tissue. If archival tissue is not available then, fresh biopsy will be done.

3. Be willing to provide tissue from a newly obtained core or excisional biopsy of a tumor lesion (in case archival tissue is not available);
4. Patients must have measurable disease based on RECIST v1.1;
5. ≥ 18 years of age;
6. Patients must exhibit a/an ECOG performance status of 0-1;
7. Life expectancy of at least 6 months;
8. Patients must have adequate organ and bone marrow function within 28 days prior to registration, as defined below:
 - leukocytes $\geq 3,000/\text{mcL}$;
 - absolute neutrophil count $\geq 1,500/\text{mcL}$;
 - platelets $\geq 100,000/\text{mcL}$;
 - total bilirubin: within normal institutional limits;
 - AST(SGOT) & ALT(SPGT) $\leq 2.5 \times$ institutional upper limit of normal (ULN) (applicable to all patients, irrespective of liver disease or metastasis); and
 - creatinine: within normal institutional limits.
9. Clinically normal resting 12-lead ECG at Screening Visit or, if abnormal, considered not clinically significant by the Principal Investigator.

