Imaging scans to be done approximately every 3 months or according to institution's standard practice.

- Time to new metastases (TTNM);

Note: Recorded time from baseline metastatic disease (at time of enrollment) to the time of development of new metastasis in different site. New metastases in same site will be also recorded.

- The change from baseline in circulating tumor cells (CTC) level in the peripheral blood.

Note: Reported unit of measure will be the number of CTCs/milliliter. CTCs enumeration will be performed at baseline and at the time of response assessment. Fraction of baseline positive and change from ≥ 5 CTCs will be recorded and reported.

- Overall survival defined as time in months from the date of first study treatment to the date of death;

Note: Patients will be followed from the start of treatment until 2 years post-treatment or death, whichever occurs first, and average survival time will be measured.

Exploratory Outcome (Endpoints) Measures:

- Measure immune biomarkers in CTCs, metastatic tissue and immune cells such as CAML and correlate with therapeutic benefit (PFS); and
- Assess changes in CTCs and CAML after treatment and perform correlative analysis of CCR5 expression.

PFS will be calculated using Kaplan-Meier curves and the median PFS will be read from this curve. Response rates (overall response rate, clinical benefit rate) will be calculated using proportions and 95% confidence intervals. Time to new metastases and overall survival will also be analyzed using Kaplan-Meier curves. Exploratory serial blood markers will be related to PFS using Cox regression, and to response using logistic regression.

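### A CTC is counted only if it is cytokeratin positive, yet any solid tumour may enrol and the CTC results use the whole Evaluable population, so non-epithelial tumours may be under-counted and handled as CTC negative

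*Protocol*

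**What the plan says.** **Assay.** Protocol 7.11.1.3 describes a filter that "isolates circulating tumor cells (CTCs) and circulating cancer-associated macrophage-like cells (CAMLs) by size exclusion", so capture does not depend on a tumour marker. Identification does. The stain mixture is "FITC-conjugated anti-cytokeratin 8, 18, 19, phycoerythrin (PE)-conjugated CCR5, and Cyanine5-conjugated CD45", and the rule for calling a cell is "CTCs are CD45 negative cells with a pleomorphic nucleus and a filamentous cytokeratin positive phenotype". DAPI, also named there, is a nuclear stain. Cytokeratin is therefore the only stain in the rule that marks tumour lineage.

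**Who enrols.** Protocol 3.2 targets "subjects with histologically or cytologically confirmed diagnosis of CCR5+ locally advanced or metastatic solid tumors". Inclusion criterion 1 in Protocol 3.3.1 is equally open: "Must have a histologically or cytologically confirmed diagnosis of locally advanced or metastatic solid tumors". Neither section restricts entry to carcinoma.

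**What is reported.** Protocol 8.7.3 and SAP 2.7.1 list as an efficacy outcome "The change from baseline in circulating tumor cells (CTC) level in the peripheral blood" and add "Fraction of baseline positive and change from ≥ 5 CTCs will be recorded and reported". SAP 8.2.1.4 plans descriptive summaries and ANCOVA. Protocol 8.7.3 also relates serial blood markers to PFS by Cox regression and to response by logistic regression, as exploratory work.

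**In whom.** SAP 6.1 and 8.2 run efficacy on the Evaluable population: treated subjects whose disease was measurable at entry. The opening of SAP 8 names an ITT set instead, but attaches no histology condition to it. SAP 7.9 prespecifies no subgroup. No section separates a tumour that the assay cannot identify from a blood sample without tumour cells.

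**The concern.** Cytokeratins 8, 18 and 19 are epithelial markers. A rule that requires them suits a carcinoma study. In a basket open to all solid tumours, a subject with, for example, a sarcoma or melanoma may have circulating tumour cells that stay on the filter but cannot be called CTCs. That subject may read zero, or too low, at baseline and at each later draw, whatever happens to the disease. Under the general efficacy rule those readings enter the CTC summaries as true negatives.

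Two results then depend on which tumours happened to enrol as well as on the drug: the proportion positive at baseline and the mean change over all subjects. The same readings enter the exploratory marker models as low counts. This matters because Protocol 1.2.2 treats the CTC count as a stand-in for metastasis and for treatment effect, and associates a low count with better outcome.

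**Working it through.** The plan gives no figure to reproduce. The sample size of up to 30 rests on clinical judgment (Protocol 8.2, SAP 3), and no expected CTC-positive rate, mean, SD or tumour mix is stated.

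**Inputs**
- N = 30, from the documents.
- k = number of subjects whose tumour cells the assay cannot identify. Not given; assumed range 0 to 9. Each is taken to read zero throughout, which is the extreme case; partial under-counting does less.
- p = fraction positive at baseline among the other N − k subjects. Not given; assumed 0.30, 0.50 or 0.70.
- d = mean change among the other N − k subjects. Left general.

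**Formulas**
- Expected positive fraction over all 30 = p × (30 − k)/30.
- Expected mean change over all 30 = [(30 − k) × d + k × 0]/30 = d × (30 − k)/30.

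| k | (30 − k)/30 | p = 0.30 | p = 0.50 | p = 0.70 |
|---|---|---|---|---|
| 0 | 1.000 | 0.30 | 0.50 | 0.70 |
| 1 | 0.967 | 0.29 | 0.483 | 0.677 |
| 3 | 0.900 | 0.27 | 0.45 | 0.63 |
| 6 | 0.800 | 0.24 | 0.40 | 0.56 |
| 9 | 0.700 | 0.21 | 0.35 | 0.49 |

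The second column is also the factor on the mean change.

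**Size against sampling error.** With k = 6 and 12 positive subjects, the all-subject figure is 12/30 = 40% (exact 95% CI 22.7 to 59.4). The figure in assessable subjects is 12/24 = 50% (29.1 to 70.9). The 10-point shift is systematic, but smaller than the width of either interval.

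**Effect on a test.** Assume a mean change of −2 and an SD of 5 in assessable subjects, with k = 6. Over all 30 the mean is 0.8 × (−2) = −1.6 and the variance is 0.8 × 25 + 0.8 × 0.2 × 4 = 20.64, so the SD is 4.543 and t = −1.6/(4.543/√30) = −1.93. In the 24 alone, t = −2/(5/√24) = −1.96. The estimate moves by a fifth; the test statistic hardly moves.

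**Chance that it arises.** This depends on the non-epithelial share of enrolment, which is also assumed (binomial, n = 30).

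| Share | P(at least 1) | P(at least 3) |
|---|---|---|
| 2% | 0.455 | 0.022 |
| 5% | 0.785 | 0.188 |
| 10% | 0.958 | 0.589 |
| 20% | 0.999 | 0.956 |

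**What is not touched.** A subject who reads zero at baseline cannot be among those starting at 5 or more, so the change in that group is not diluted. PFS, ORR, CBR, TTNM and OS do not use the count.

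**The case against.** The strongest reply is that the documents never say which tumours lack these cytokeratins. A reader might infer that every non-epithelial subject is a guaranteed zero. The documents do not support that: the premise is general pathology, is not universal, and justifies only saying that such subjects may be under-counted. This limit stands. The gap remains, because the counting rule requires cytokeratin and nothing covers tumours without it.

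Second, no affected subject is shown, and k could be 0. That stands too, and is why the range starts there.

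Third, a reader might infer that every CTC change measure is distorted. The change from 5 or more is not, so only the all-subject summary or ANCOVA, the positive fraction and the marker models are exposed.

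Fourth, no sentence states a CTC-specific denominator. That is correct: the all-subject reading follows from the general Evaluable rule together with silence in SAP 8.2.1.4. It is an omission, not a declared choice.

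Fifth, the consequence is limited. The study is single-arm, SAP 5 disclaims formal hypothesis testing, and no decision rule uses CTCs. Zeros pull the mean change toward no change, so they cannot by themselves create an apparent fall. Listings and ad hoc subgroups (SAP 7.9) would allow a later split. That lowers the stakes, but a split chosen after the counts are known is weaker than one fixed beforehand. It also needs histology data, which Protocol 7.3 does not clearly collect.

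Finally, the marker models are exploratory and appear only in the Protocol; SAP 8.4.1 plans descriptive summaries. The effect on those models has not been quantified.

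**Conclusion.** The concern holds as a gap in the definition of the CTC analysis set. The plan counts only cytokeratin-positive cells, admits tumours that may not express cytokeratin 8, 18 or 19, and has no rule for them. Where k of 30 subjects cannot be counted, the baseline-positive fraction and the all-subject mean change fall to (30 − k)/30 of their value in assessable subjects: no loss at k = 0, about 3% at 1, 10% at 3, 20% at 6 and 30% at 9.

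This rests on three assumptions that the documents do not supply: the value of k, the cytokeratin status of non-epithelial tumours, and a reading of zero throughout for the affected subjects. It bears on one efficacy outcome and on exploratory models. It is worth correcting while the SAP is, by its own version history, a first draft.

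**What to change.** 1. **Protocol 7.3:** add primary site and histology (carcinoma or not), taken from the pathology report already needed for eligibility. At present the section lists breast-type morphology categories plus Other and Unknown, with no primary site, and the pre-screening log in Protocol 4.1.1 has no histology entry. SAP wording alone would therefore not be enough.
2. **SAP 8.2.1.4 and 8.4:** before any count is seen, define a CTC-evaluable set as Evaluable subjects with an epithelial (carcinoma) primary. Use it for the baseline-positive fraction, the CTC change and the CTC marker models. Define it by histology rather than by baseline count, because selecting on the count would add regression to the mean.
3. **Other subjects:** list their counts, marked as possibly not assessable by this assay, and show the all-Evaluable summary alongside.

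The cost is one data field, a few lines of SAP text and a smaller CTC set. Carcinoma is only a proxy for cytokeratin expression, so some misclassification will remain; the side-by-side summaries let a reader see how far the choice of set matters. If no non-epithelial tumour enrols, the two sets coincide and no subject is lost from the CTC set.

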7.12 STUDY TREATMENT APPLICATION

Refer to [Section 6.1](#) for details.

7.13 POST-INJECTION EVALUATION AND INJECTION SITE REACTION ASSESSMENT

[figure not shown]
At each treatment visit, an injection site reaction assessment will be made for the current and previous injection sites. Injection site reaction assessments are recorded by the Investigator starting after the first injection is given. Subject will be observed at approximately 30 minutes post-injection or longer if necessary for injection site reaction as per CTCAE v5.0. Refer to [Sections 9.2.6](#) for more details.

7.14 PAIN NUMERIC RATING SCALE

Pain will be assessed using a 10-point Numeric Rating Scale from 0 to 10 with 0 meaning no pain and 10 pain as bad as you can imagine

Figure 7-1: Numeric Rating Scale

0–10 Numeric Pain Rating Scale

7.15 TUMOR IMAGING AND RESPONSE EVALUATION

For the purposes of this study, patients should be re-evaluated for tumor response approximately every 3 months or according to institution's standard practice. In addition to a baseline scan, confirmatory scans should also be obtained 6 weeks following initial documentation of objective response greater than Stable Disease (SD).

Response and progression will be evaluated in this study using the new international criteria proposed by the revised Response Evaluation Criteria in Solid Tumors (RECIST) guideline (version 1.1). Changes in the largest diameter (unidimensional measurement) of the tumor lesions and the shortest diameter in the case of malignant lymph nodes are used in the RECIST criteria.

High resolution CT with oral/intravenous contrast or contrast-enhanced MRI is the preferred imaging modalities for assessing radiographic tumor response. If a subject has a known allergy to contrast material, please use local prophylaxis standards to obtain the assessment with contrast if at all possible, or use the alternate modality. In cases where contrast is strictly contraindicated, a non-contrast scan will suffice. Screening assessments should be performed within 28 days of registration. Brain MRI is the preferred imaging method for evaluating CNS metastasis, and

assessment is required during screening in all eligible subjects. All known or suspected sites of disease (including CNS if history of CNS metastases) should be assessed at screening and at subsequent assessments using the same imaging method and technique. If more than one method is used at screening, then the most accurate method according to RECIST v1.1 should be used when recording data, and should again be used for all subsequent assessments. Previously treated CNS metastases are not considered measurable lesions for purposes of RECIST determined response. Subjects with a history of brain metastasis should have surveillance MRI approximately every 12 weeks, or sooner if clinically indicated.

Radiographic tumor assessments will be conducted approximately every 3 months or according to institution's standard practice by CT or MRI (per treating investigator's discretion); the same modality used at baseline should be used throughout. Tumor measurements will be done using RECIST v1.1. Tumor assessments for all subjects should continue as per protocol even if dosing is interrupted. Tumor measurements should be made by the same investigator or radiologist for each assessment whenever possible. Changes in tumor measurements and tumor responses to guide ongoing study treatment decisions will be assessed by the investigator using RECIST.

7.15.1. Definition of Lesions

Tumor response will be assessed according to the RECIST (version 1.1; *Eisenhauer et al. 2009*). At baseline, tumor lesions/lymph nodes will be categorized measurable or non-measurable as follows:

Measurable disease

Measurable lesions are defined as those that can be accurately measured in at least one dimension (longest diameter to be recorded) as ≥ 20 mm (≥ 2 cm) by chest x-ray or as ≥ 10 mm (≥ 1 cm) with CT scan, MRI, or calipers by clinical exam (such measurements must be clearly documented). All tumor measurements must be recorded in millimeters (or decimal fractions of centimeters).

Malignant lymph nodes:

To be considered pathologically enlarged and measurable, a lymph node must be ≥ 15 mm in short axis when assessed by CT scan (CT scan slice thickness recommended to be no greater than 5 mm). At baseline and in follow-up, only the short axis will be measured and followed.

Non-measurable disease

All other lesions (or sites of disease), including small lesions (longest diameter < 10 mm or pathological lymph nodes with ≥ 10 to < 15 mm short axis) as well as truly non-measurable lesions.

Bone lesions, leptomeningeal disease, ascites, pleural/pericardial effusions, lymphangitis cutis/pulmonitis, inflammatory breast disease, and abdominal masses (not followed by CT or MRI), are considered as non-measurable.

Special considerations regarding lesion measurability

Bone lesions, cystic lesions, and lesions previously treated with local therapy require particular comment:

Bone lesions:

- Bone scan, PET scan or plain films are not considered adequate imaging techniques to measure bone lesions. However, these techniques can be used to confirm the presence or disappearance of bone lesions.
- Lytic bone lesions or mixed lytic-blastic lesions, with identifiable soft tissue components, that can be evaluated by cross sectional imaging techniques such as CT or MRI can be considered as measurable lesions if the soft tissue component meets the definition of measurability described above.
- Blastic bone lesions are non-measurable.

Cystic lesions:

- Lesions that meet the criteria for radiographically defined simple cysts should not be considered as malignant lesions (neither measurable nor non-measurable) since they are, by definition, simple cysts.
- ‘Cystic lesions’ thought to represent cystic metastases can be considered as measurable lesions, if they meet the definition of measurability described above. However, if noncystic lesions are present in the same patient, these are preferred for selection as target lesions.

Lesions with prior local treatment:

- Tumor lesions situated in a previously irradiated area, or in an area subjected to other loco-regional therapy, are usually not considered measurable unless there has been demonstrated progression in the lesion. Study protocols should detail the conditions under which such lesions would be considered measurable.

